Shoulder surgery has evolved over the past decade with many procedures now done on an outpatient basis. Multimodal pain management strategies and regional anesthesia have greatly contributed to this transition and newer strategies continue to evolve. Uncontrolled pain can often lead to readmissions, prolonged hospital or ambulatory stays and an overall negative patient experience. Despite improvements in regional anesthetic technique and newer longer acting medicines such as liposomal bupivacaine, the duration of pain relief is often only over the course of 72 hours postoperatively. Post-operative pain beyond 72 hours is largely inflammatory in nature. As such, biologic approaches to reduce surgical tissue damage-induced inflammation is an attractive therapeutic addition to surgical procedures. These approaches are especially relevant in light of the current opioid epidemic plaguing the United States.

Flowable, placental-derived connective tissue matrix (pECM) is a potential option to supplement damaged tissue prone to inflammation as it introduces nascent, hydrated components of the inflammatory phase, including structural proteins and growth factors, which allow for efficient repair. Derived from relatively immune-privileged tissue, placental-derived pECM elicits little or no immune response in recipients. They have been shown to greatly reduce inflammatory cell influx and inflammatory cytokines present in dermal and mucosal surgical sites post-operatively. Moreover, placental-derived pECM reduces expression of prostaglandin E2, a potent pain mediator, *in vitro*. In the orthopedic space, ECM has been used effectively to reduce pain following spinal fusion and for treatment of knee arthritis. Taken together, biologic therapies directed at modulating inflammation and associated pain is an increasing area of interest with far reaching implications.

The purpose of the current study is to prospectively analyze two groups of patients treated for rotator cuff repair with and without a flowable pECM to determine if a significant reduction in pain and opioid consumption as measured in morphine equivalent units is demonstrated within the first 6 weeks of surgery. Furthermore, patients will be compared in regard to early range of motion and patient reported outcomes to determine if a difference is present when the ECM is utilized within the first 6 months of surgery. This is the first double blinded prospective series in the shoulder literature to date looking at a pECM graft for pain reduction and improved range of motion perioperatively.

Study Objectives

Utilizing a prospective randomized controlled trial, the aim of this study is to assess modulation of post-operative pain and narcotic use when a placental-derived extracellular matrix is injected into the bed of the repair following outpatient rotator cuff repair surgery. Furthermore, this study aims to determine if the addition of pECM influences patient reported outcomes and influences early postoperative range of motion.

Primary Aims & Objective

Aim 1a: To assess post-operative narcotic consumption (measured in morphine equivalent units) between patients treated with flowable placental-derived pECM compared to those patients undergoing rotator cuff surgery.

Hypothesis: Narcotic consumption (measured in morphine equivalent units) will be reduced in patients treated with an extracellular matrix graft as compared to those patients undergoing rotator cuff surgery without.

Objective: Utilizing a prospective randomized controlled trial, narcotic use will be measured for 12-hour increments for a total of 7 post-operative days (PODs) then once on POD 14, 21, 28, and 42. Consumption will be measured by the number of tablets ingested and converted to morphine equivalent units and compared between the two treatment groups.

Aim 1b: To determine if flowable placental-derived pECM decreases patient-reported post-operative VAS pain in patients undergoing outpatient rotator cuff surgery

Hypothesis: There will be a decrease in VAS pain for up to 6 weeks post-operatively among participants who receive pECM, as compared to the control group (no pECM).

Objective: Utilizing a prospective randomized controlled trial, post-operative patient-reported VAS pain (on a scale of 0-10) will be collected 2 times per day (every 12 hours) for 7 post-operative days (PODs); then an average score collected on POD 14, POD 21, POD 28, and POD 42. Scores will be averaged and compared between the two treatment groups for the first 7 days, 2 week, 3rd week, 4th week and 6th week postoperatively.

Secondary Aims & Objectives

Aim 2a: To assess patient-reported outcomes and early range of motion (measured in morphine equivalents) in patients treated with flowable placental-derived pECM compared to patients injected with saline control.

Hypothesis: There will be improved patient reported outcomes and early range of motion measured at 6 weeks and 3 months and 6 months postoperatively in patients receiving and extracellular matrix injection following outpatient rotator cuff surgery.

Objective: Utilizing a prospective randomized controlled trial, patient reported outcomes as measured by American Shoulder and Elbow Score, Simple Shoulder Test and SANE scores and range of motion (External rotation, internal rotation and forward flexion) will be collected preoperatively and at 2 weeks (external rotation), 6 weeks (all) , 3 months (all) and 6 months (all) postoperatively. Scores and range of motion measurements will be averaged and compared for differences between the two groups.

Study Design

The study design is a randomized double-blind randomized controlled trial.

Research Design

Patients will be randomly assigned to one of two treatment groups (see Intervention Description). Patients will randomly select one of 70 sealed envelopes the day of surgery. Patients will be blinded to the medication utilized as well as the treating surgeon (PI). A consecutive series of patients will be enrolled to prevent selection bias. A single surgeon will be performing all procedures to minimize variability. Upon completion of the surgery, a spinal needle will be loaded into the substance of the rotator cuff tendon under direct arthroscopic visualization. The surgeon will then leave the room and the envelope will be opened by the circulating operating room nurse. If the patient is in the treatment group, 2cc of an extracellular matrix graft be opened and then injected with a 22g spinal needle already placed into the bed of the repair by the physician assistant. Those patients that are in the control group will have the needle removed and no injection administered. The envelope will be then sealed with the patient's name and treatment group to allow for data analysis upon completion of the study.

Data Collection will occur post-operatively for 6 months. Data will be collected at 20 timepoints, in total for pain and opioid consumption. For the first seven days, data will be collected at 12-hour time intervals beginning the first evening of the surgery (POD0) at 8pm then at 12-hour intervals for the next 7 days (POD7). Data will be collected using PatientIQ, an application that uses text message or email to collect information. The day of surgery (POD0) the first text will occur at 8pm. Patients will then be notified by text alert 2 times per day (8am and 8pm) asking to rate their pain on a scale of 0-10 (VAS) beginning on POD 1 thru POD 7. Patients will also respond to the number of pain pills taken in the slotted time span. All patients will be prescribed the same narcotic regimen (oxycodone IR) barring any allergies encountered. Patients who fail to respond to the text alert will be notified by the data collection system and contacted via phone by study personnel. Patients lacking smartphone technology will all be notified via telephone and also asked to keep a personal log to capture the information needed.

Data Management

Patient IQ is password protected and HIPPA compliant data collection system. Patients upon enrollment will be assigned an ID to allow for data tracking within the application. The application does not have access to other personal information on the patient's electronic device. Primary data will be collected via the web-based system and stored electronically and encrypted under password protection. The principal investigator will only have access to the database. At the conclusion of the study, the data will be exported to a password-protected encrypted Excel file on a password-protected computer. Once the data have been checked for accuracy and prior to statistical analysis, patient identifiers will be removed from the data set. The de-identified password-protected Excel spreadsheet will be provided to a statistician who will import the file into SPSS for analysis.

Study Agent, Device, and/or Intervention Description

The pECM graft administered at completion of the surgery is the intervention in this study. Study participants will be randomized into one of two groups. The treatment groups are listed below:

Group 1 (Control)	Group 2
Standard rotator cuff repair and no pECM injection	Rotator cuff repair and 2cc of pECM injection into perimeter of repair

Sample Size

For an analysis of variance (ANOVA) test, a sample size of 28 participants per group would be required, given an effect size of $f=0.30$ a power of 80%, and a two-tailed alpha level of 0.05. However, to account for 20% subject attrition, a total of 35 patients per group will be enrolled, yielding a total of 70 participants.

Subject Selection

Patients who meet the following criteria will be included in the study:

Inclusion Criteria

1. Age 18 and older
2. Primary diagnosis of rotator cuff tear
3. Able to provide informed consent
4. Is willing and able to accept text messages

Patients who meet the following conditions will be excluded from participation:

Exclusion Criteria

1. Older than 55 years old.
2. Pregnancy.
3. Known narcotic or alcohol abuse (< 3 months)
4. Revision rotator cuff surgery
5. Current narcotic regimen or contract with pain management specialist

Study Outcome Measures (Endpoints)

Primary Endpoint: Patient-reported post-operative VAS pain (on a scale of 0-10), measured post operatively, in 12-hour increments, for a total of 7 days postoperatively and then once per day on POD 14, 21, 28 and 42.

Patients will be prompted via text message to provide VAS pain every 12 hours for the first 7 days and then once per day at later timepoints. If a response text message is not received, a phone call will be made to obtain the information. Patients who do not have a smart phone will receive a phone call or keep a personal log of VAS pain.

Secondary Endpoint: Patient-reported post-operative opioid use (converted to morphine equivalents), collected post operatively, in 12-hour increments for the first 7 days and then once per day on POD 14, 21, 28 and 42.

Patients will be prompted via text message to provide the amount of narcotics (number of pills converted to morphine equivalents) taken over the course of the previous 12 hours. If a response text message is not received, a phone call will be made to obtain the information. Patients who do not have a smart phone will receive a phone call or keep a personal log of narcotic use.

Study Procedures

Subject Recruitment and Screening

Participants will be recruited from the clinical practice of [name]. Patients who present for an office visit and are diagnosed with a rotator cuff tear requiring outpatient surgical intervention will be screened for eligibility for participation in the study. If a patient is eligible for the study, [name] will discuss the study with the patient and obtain informed consent during the routine office visit.

Randomization

This is a double-blinded study, thus, neither the surgeon nor the patient will know if a pECM injection is used. A total of 70 envelopes will be generated consisting of 35 with Group 1” (no pECM) and 35 with “Group 2” (pECM Injection). Envelopes will be sealed and randomly chosen prior to surgery. Once the envelope is opened to determine if pECM is to be injected, the name of the patient will be added to the envelope along with the treatment group, and the envelope will be sealed. The treatment group and name of patient will be kept confidential until completion of the study. Envelopes will be opened at end of study for data collection and analysis purposes with patient information deidentified. They will be stored in a locked container at the surgery center only accessible by the chief of staff. Patients will be blinded to the treatment as well as the treating surgeon. The physician assistant will not be blinded as she will administer the injection for the treatment group but will keep the information confidential. She will not participate in follow-up data collection of the patients in this study postoperatively.

Study Visits/ Study Duration

Participants enrolled in this study will be followed for a period of 6 months post-operatively. For the first week, twice per day (12-hour increments), patients will self-report VAS pain and indicate their narcotic use (number of tablets ingested). Data concerning pain and narcotic use will be collected via text message (or phone if patients fail to respond to text messages).

Post-operative day (POD)	Data Collection Time	Data to be Collected
POD 0	8PM	VAS; #pain pills used
POD1	8AM	VAS; #pain pills used
	8PM	VAS; #pain pills used
POD2	8AM	VAS; # pain pills used
	8PM	VAS; # pain pills used
POD3	8AM	VAS; # pain pills used
	8PM	VAS; # pain pills used
POD4	8AM	VAS; # pain pills used
	8PM	VAS; # pain pills used
POD5	8AM	VAS; # pain pills used
	8PM	VAS; # pain pills used
POD6	8AM	VAS; # pain pills used
	8PM	VAS; # pain pills used

POD7	8AM	VAS; # pain pills used
	8PM	VAS; # pain pills used
POD14 (2 weeks)	Office Exam	ER (neutral); ASES; SANE; SST
	8PM	VAS; # pain pills used
POD21 (3 weeks)	8PM	VAS; # pain pills used
POD28 (4 weeks)	8PM	VAS; # pain pills used
POD42 (6 weeks)	Office Exam	ER (neutral and scapular/IR- scapular/FF; ASES; SANE; SST
	8PM	VAS; # pain pills used
3 months	Office Exam	VAS; ER (neutral and scapular/IR-scapular/FF; ASES; SANE; SST
6 months	Office Exam	VAS; ER (neutral and scapular/IR-scapular/FF; ASES; SANE; SST

The enrollment period for study participation is anticipated to last for 12 months only for data analysis.

Specimen Collection, Preparation, Handling and Shipping

N/A

Statistical Analysis Plan

After data checking and validation are completed, the analysis of the data will begin with examination of the distribution of each of the study variables. In this process, outliers will be identified and evaluated for inclusion in the final study database. Appropriate summary statistics will be calculated. Means and standard deviations will be reported for normally distributed continuous variables, a median and range will be tabulated for continuous variable that are not normally distributed, and frequencies and percentages will be provided for categorical variables. The remainder of the analysis will correspond to the specific aims provided above.

Specific Aims 1a-b:

To determine if there is a difference in patient-reported post-operative narcotic use (measured in morphine equivalents) among two groups.

If data are normally distributed, analysis of variance (ANOVA) with Tukey's HSD pairwise comparisons will be used to compare narcotic use (converted to morphine equivalents) between the three groups at each PODs. Cumulative narcotic use during all PODs will also be compared between groups. If data are not normally distributed, then Kruskal-Wallis with Dunn's multiple comparisons tests will be used.

To determine if there is a difference in mean VAS pain between the control group and ECM group postoperatively.

If data are normally distributed, analysis of variance (ANOVA) with Tukey's HSD pairwise comparisons will be used to compare VAS pain between the two groups at each PODs 1-7, 14, 21, 28 and 42. If data are not normally distributed, then Kruskal-Wallis with Dunn's multiple comparisons tests will be used.

Specific Aim 2:

To determine if there is a difference in clinical and functional outcomes of patients with rotator cuff tears treated with the nanofiber scaffold compared to those treated without.

If data are normally distributed, independent t-tests will be used to compare VAS Pain, SANE, V-12, ASES, and ROM measures between the control and intervention groups at each preoperative and postoperative timepoint. If data are not normally distributed, then Mann-Whitney U tests will be performed.

Potential Risks and Benefits

Potential Risks

This research is collecting data on human tissue implants which are routinely used in surgical repair. They are all FDA registered. The following risks can be related to the procedure, study analysis, and medications given:

1. Risk of extracellular matrix injection: Like any medical procedure, there are risks associated with the procedure itself. Theoretical risks associated with the extracellular matrix injection include infection, allergic reaction and injection site irritability. These risks are inherently low risks associated with administration.
2. Risk of text alerts: A HIPPA compliant and password protected database called Patient IQ is the application that will help gather and collect the data. Texting is not a secure form of communication and there is a risk of loss of privacy by entering the data. Measures to lessen these risks include using a password protected database and all personal information will be deidentified with your name removed. In addition, the only information you will provide will be regarding pain level and number of pain pills taken. Your phone number will be kept confidential and not shared with any outside party.

Potential Benefits

An individual benefit from this study is that patients will be monitored closely via text messages two times per day; thus, if any side effects or complications occur related to the injection, the PI will be alerted. Additionally, knowledge gained from this study will allow investigators to determine the most effective treatment methods for minimizing post-operative pain and narcotic use in patients who undergo outpatient rotator cuff surgery. These findings will benefit future patients.

Adverse Event Reporting:

Adverse Events

Recording of Adverse Events

At each contact with the subject, the investigator will seek information on adverse events by specific questioning and, as appropriate, by examination. Information on all adverse events should be recorded immediately. All clearly related signs, symptoms, and abnormal diagnostic procedures results should be recorded in the source document.

Notification of Adverse Events

All adverse events will be reported according to WIRB guidelines.

Ethical Considerations

N/A

Funding Source

N/A

Subject Stipends or Payments

N/A

Publication Plan

The paper will be submitted for publication in the Journal of Shoulder and Elbow Surgery or the Journal of Bone and Joint Surgery upon completion.

References

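### Aim 1a is one claim about opioid use, but the SAP tests it at each POD and again as a cumulative total without saying which test decides it

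*Combined protocol and SAP*

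**What the plan says.** The hypothesis under Aim 1a is one statement: "Narcotic consumption (measured in morphine equivalent units) will be reduced in patients treated with an extracellular matrix graft". The Secondary Endpoint paragraph collects opioid use "in 12-hour increments for the first 7 days and then once per day on POD 14, 21, 28 and 42".

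For the analysis, Specific Aims 1a-b of the Statistical Analysis Plan will "compare narcotic use (converted to morphine equivalents) between the three groups at each PODs. Cumulative narcotic use during all PODs will also be compared". The method is ANOVA with Tukey's HSD, or Kruskal-Wallis with Dunn's tests if the data are not normal. The opioid sentence does not list its days. The only list is the one for VAS pain, which names PODs 1-7, 14, 21, 28 and 42. The Study Visits table also schedules a tablet count on the evening of POD 0.

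The sentence speaks of three groups, but the trial has two: "A total of 70 envelopes will be generated consisting of 35 with Group 1" and the other 35 for Group 2. The significance level appears only in the Sample Size section ("a power of 80%, and a two-tailed alpha level of 0.05") and is not divided among tests. Nothing in the document ranks the daily comparisons against the total.

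**The concern.** One claim has a dozen or more tests behind it and no rule for combining them. A report that followed the plan as written could present reduced opioid use on the strength of one isolated day while total consumption did not differ. Nothing in the SAP would show that this was not the planned answer. The daily tests come first in the text and the total is added afterwards, so the daily tests cannot be assumed to be descriptive.

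The named post-hoc procedures look like multiplicity control, but they work across groups and not across days.

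The problem lies within the opioid endpoint. It remains whether opioid use is a primary aim (as under Primary Aims & Objective) or the secondary endpoint (as under Study Outcome Measures), and however the VAS timepoints are handled. Reduced opioid use is a headline purpose of the trial, so it matters which result may carry that claim.

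**Working it through.** **The plan's own figures.** The documents state no error rate across tests, so there is none to reproduce. The Sample Size section gives "a sample size of 28 participants per group would be required" and "to account for 20% subject attrition, a total of 35 patients per group will be enrolled". The attrition step reproduces: 28/(1 − 0.20) = 35. The 28 does not. For a two-group one-way ANOVA with f = 0.30, the noncentrality at 28 per group is 56 × 0.30² = 5.04 on 1 and 54 df, giving 60% power; 80% needs 45 per group. That is a separate matter. Here 28 serves only as the evaluable number that the plan expects, and each test runs at 5% under no effect whatever the group size.

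**Step 1: count the tests.** POD 0-7 is 8 days; POD 14, 21, 28 and 42 add 4, making 12. Without POD 0, as in the VAS list, there are 11. Adding the total gives 13 or 12 tests. If every scheduled report were tested, there would be 1 + 7 × 2 + 4 = 19, plus the total.

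**Step 2: what Tukey and Dunn adjust.** With g groups there are g(g − 1)/2 pairwise comparisons. At g = 2 that is one, so neither procedure changes any p-value, and neither acts across days.

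**Step 3: upper reference.** If the tests were independent, the chance of at least one p<0.05 would be 1 − 0.95^12 = 46.0% for 12 tests and 1 − 0.95^13 = 48.7% for 13. Days within a patient are correlated, so the true figure is lower.

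**Step 4: simulation with correlated days.** The settings were 28 per group, no group effect, K normal daily values per patient with equal correlation ρ, and the total taken as their sum. Each test is t = |difference in means| / (s_p √(2/28)) on 54 df, two-sided at 0.05, which is identical to a two-group ANOVA. There were 20,000 trials per setting. The documents give no ρ, so every value is an assumption. Chance of at least one p<0.05, in either direction:

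| ρ | 11 PODs + total | 12 PODs + total |
|---|---|---|
| 0.3 | 37.8% | 39.5% |
| 0.5 | 30.0% | 31.8% |
| 0.7 | 22.6% | 23.6% |
| 0.8 | 18.2% | 19.3% |
| 0.9 | 13.3% | 13.5% |

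Separate reruns agree within about a percentage point. Together with rank tests on skewed data (33% for 12 PODs at ρ = 0.5), they give 30-33% at ρ = 0.5 and about 14% at ρ = 0.9.

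**Step 5: direction.** These rates count differences either way. Counting only those that favour pECM gives about 15-17% at ρ = 0.5, against a nominal 0.05/2 = 2.5%.

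**Step 6: other assumptions.**
- Correlation that decays with visit order (AR(1)), 11 PODs plus total: 39% at 0.5, 33% at 0.7, 20% at 0.9.
- All 19 reports plus the total, equal correlation: 52% at 0.3, 42% at 0.5, 29% at 0.7.
- Tablet counts with many zeros (assumed Poisson, means falling over time, 64-91% zeros on the last four days, 5,000 trials): at a mean between-day correlation of 0.52, 36% by rank test and 30% by t-test; at 0.23, 43% and 38%. In 31-40% of these null trials some single day was significant by rank test while the total was not.

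**Step 7: the total alone.** In the simulations with normal or skewed data, the cumulative test by itself rejected in 4.7-5.5% of null trials. It also stayed near 5% with the zero-heavy counts.

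**The case against.** The strongest reply is that the plan never says that any significant day settles Aim 1a. A claim about consumption maps most naturally to the cumulative comparison, which is already planned and holds its 5%. The endpoint section also ranks opioid use as secondary, where unadjusted daily tests are common. On this view one clarifying sentence is missing, and no error has been committed.

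Much of that stands. A reader might infer that this trial has a 32% chance of falsely claiming reduced opioid use. The documents do not support that, for three reasons:
- The figure needs an assumed correlation near 0.5 and a count of days that the opioid sentence does not give.
- It counts differences in both directions, so false results favouring pECM are about half as frequent.
- It applies only if any single p<0.05 is taken as the answer, a rule that the documents neither state nor exclude.

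A reader might also count it as a harm that the trial could report no reduction from the total when one day is significant. That is simply what follows once the total decides, so it is not a second defect.

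The reply does not remove the gap. The natural reading is not written down. The rank of opioid use is contradictory, because Aim 1a stands under the primary aims. The wording places the daily tests first. Many zero-opioid days and rank tests might have been expected to lower the rate, but the check in Step 6 shows no material fall.

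**Conclusion.** The point holds in a conditional form. The plan tests one claim 12 or 13 times, names no deciding test and makes no adjustment across days. If any p<0.05 is read as the answer, the chance of a spurious opioid difference in either direction is about 30-33% at an assumed between-day correlation of 0.5, and runs from about 14% (0.9) to 40% (0.3). About half of these would favour pECM. In no setting tried does the any-test rate come near 5%; the cumulative test alone does.

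The size rests on assumed correlations, 11 or 12 tested days, 28 evaluable patients per group and the any-test reading. The absence of a deciding test rests on none of these. This should be corrected because it governs what may be claimed; it does not invalidate the trial.

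**What to change.** Before the envelopes are opened for analysis, add to Specific Aims 1a-b:

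> Aim 1a is decided by one test: the between-group comparison of cumulative morphine equivalents, at two-sided 0.05. Comparisons at individual PODs are descriptive, are shown as group differences with 95% confidence intervals, and do not support a claim of reduced consumption.

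State the window of the total in the same place. There are two candidates:
- **All PODs.** This matches the current SAP text. After POD 7, however, it contains only four isolated reports. If the 12-hour recall in the Secondary Endpoint paragraph applies to them, they cover 4 × 12 = 48 hours of the 35 days from POD 8 to POD 42, so the sum is not six-week consumption and should not be called that.
- **POD 0-7.** This is the period of uninterrupted 12-hourly reporting. Choosing it changes the planned all-PODs total, and the deciding test would then not cover weeks 2-6 of the six-week purpose stated in the introduction. The amendment should say both.

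Correct the reference to three groups in the same sentence. If the team prefers to keep every test confirmatory, a Bonferroni level would be 0.05/12 = 0.0042 for 12 tests or 0.05/13 = 0.0038 for 13, at a loss of power.

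The cost is SAP wording, with no new data or visits; a POD 0-7 window would also be a declared change to the planned total. The downside is that a difference confined to a single day can no longer be claimed as the Aim 1a result.

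### The SAP's cumulative opioid total is one continuous week plus four late snapshots, not six-week consumption: 94% of the time from POD 8 to POD 42 goes unrecorded (89% if each late report covers 24 hours)

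*Combined protocol and SAP*

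**What the plan says.** The purpose statement before Study Objectives sets the horizon: the trial asks whether a reduction in "opioid consumption as measured in morphine equivalent units is demonstrated within the first 6 weeks of surgery". Aim 1a, listed among the primary aims, measures narcotic use in "12-hour increments for a total of 7 post-operative days (PODs) then once on POD 14, 21, 28, and 42". The Secondary Endpoint paragraph repeats the schedule: "in 12-hour increments for the first 7 days and then once per day on POD 14, 21, 28 and 42". That paragraph also describes the prompt, which asks for narcotics "taken over the course of the previous 12 hours". No other passage gives the recall window a length.

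Study Visits/Study Duration ties the 12-hour increments to week one: "For the first week, twice per day (12-hour increments), patients will self-report VAS pain and indicate their narcotic use". Its table then shows a single 8PM report on each of the four later days.

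For the analysis, the SAP says "Cumulative narcotic use during all PODs will also be compared between groups". It does not say which days enter the sum or how the time between late reports is treated. The neighbouring VAS paragraph lists the scheduled days, comparing pain "between the two groups at each PODs 1-7, 14, 21, 28 and 42". Nowhere is there a since-last-report question, a tablet count, a refill record or an imputation rule.

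**The concern.** A reader will take a cumulative total, reported under a six-week purpose, as the opioids used in six weeks. What the plan collects is a complete first week plus four isolated readings. On the stated window, the daily values entering the sum also differ in length: 24 hours on POD 1-7 (two reports) and 12 hours on POD 14-42 (one report).

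This bears on the trial's own rationale. The opening background text says: "Post-operative pain beyond 72 hours is largely inflammatory in nature". That is the component pECM is meant to modify. POD 3-7 is fully recorded, but nearly all tablets taken or saved after POD 7 are not.

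- **Any effect pattern:** total use is understated in both arms.
- **Effect that starts after the first days:** both the tablets saved and the percentage reduction are understated.
- **Same proportional effect from day 0:** the ratio between arms is unbiased, and only the absolute saving is understated.

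In each case the sum cannot support a statement about total six-week morphine equivalents. Tablets that were never asked about cannot be recovered later.

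**Working it through.** **1. Count the reports.** From the Study Visits table: 1 (POD 0, 8PM) + 7 × 2 (POD 1-7) + 4 (POD 14, 21, 28, 42) = 19 opioid reports. Research Design states 20 timepoints for pain and opioids, which this count does not reproduce; VAS including the 3- and 6-month visits gives 19 + 2 = 21. The mismatch hardly matters here: a twentieth report placed after POD 7 would still leave 65 of 70 half-days (92.9%) unrecorded.

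**2. Time coverage after week one.** No outside assumption is needed. The first 15 reports are back to back (15 × 12 h = 180 h), so the first week is complete. From 8PM on POD 7 to 8PM on POD 42 is 35 days = 70 half-days = 840 h.

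- 12-hour window: 4 × 12 = 48 h; 48/840 = 5.7% recorded, 94.3% unrecorded.
- 24-hour reading: 4 × 24 = 96 h; 96/840 = 11.4% recorded, 88.6% unrecorded.

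**3. From time to tablets.** The documents give no opioid trajectory, so this step is an assumption shown over a range. Let use decline exponentially over days 0-42 with half-life h, and write k = ln 2 / h. Use between days a and b is proportional to A(a,b) = exp(−ka) − exp(−kb). The late 12-hour reports contribute S = the sum of A(d − 0.5, d) over d = 14, 21, 28, 42.

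- Share of use after day 7 = A(7,42) / A(0,42)
- Recorded share of true use = [A(0,7) + S] / A(0,42)
- Recorded share of a saving from day 3 on = [A(3,7) + S] / A(3,42)
- With an assumed 30% cut from day 3: true reduction = 0.30 × A(3,42) / A(0,42); reduction seen in the sum = 0.30 × [A(3,7) + S] / [A(0,7) + S]

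Worked case, h = 5 days: k = 0.1386, A(0,42) = 0.9970, A(0,7) = 0.6211, A(7,42) = 0.3760, A(3,7) = 0.2808, A(3,42) = 0.6568, S = 0.0159.

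- Use after day 7: 0.3760 / 0.9970 = 38%.
- Recorded share: 0.6370 / 0.9970 = 64%.
- Recorded share of the saving: 0.2967 / 0.6568 = 45%.
- True reduction: 0.30 × 0.6568 / 0.9970 = 19.8%.
- Reduction seen: 0.30 × 0.2967 / 0.6370 = 14.0%.

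| Assumed half-life (days) | 2 | 3 | 5 | 7 | 10 |
|---|---|---|---|---|---|
| Use after day 7 | 9% | 20% | 38% | 49% | 59% |
| Recorded sum / true 42-day use | 91% | 81% | 64% | 53% | 44% |
| Saving from day 3 recorded, 12-hour | 75% | 62% | 45% | 37% | 30% |
| Same, 24-hour reading | 76% | 63% | 48% | 40% | 34% |
| True reduction (30% cut from day 3) | 10.6% | 15.0% | 19.8% | 22.2% | 24.0% |
| Reduction seen in the sum, 12-hour | 8.8% | 11.4% | 14.0% | 15.3% | 16.4% |

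**The case against.** **The late window may be longer than 12 hours.** Research Design refers only to pills taken in the relevant slot, with no length, and Aim 1b treats the late VAS values as averages compared by week. If each late opioid report covered the previous 7 days, 4 × 168 = 672 of 840 h would be recorded and only 20% missed; on the same tapers the sum would then hold 94% to 100% of 42-day use. If reports covered all time since the last one, nothing would be missed. It stands that the late window is not separately defined. But the slot wording follows the twice-daily prompts, the weekly wording is for VAS only, and no passage gives opioids a longer window. If one was intended, it has to be written down.

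**The SAP does not promise a six-week total.** Read with the VAS paragraph, the sum may simply run over scheduled days. That sum can be computed. It would still be labelled cumulative under a six-week purpose and could not represent that period.

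**Hours are not tablets.** This stands. With a fast taper little is lost, and the spread in the table comes from assumed half-lives. The exclusion of patients on a current narcotic regimen gives some reason not to weight the slowest tapers heavily.

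**The trial-level consequence is limited.** Both arms are measured alike, and a late effect is diluted toward no difference, so the error does not create a false positive. Unequal windows across days do not bias comparisons within a day. The Endpoints section also labels opioid use secondary. All of this holds, and it limits the severity. However, Aim 1a lists opioid use as primary, and the dilution falls on the kind of effect the rationale predicts.

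**Conclusion.** The concern holds. On the schedule and the only recall window stated, the cumulative sum contains a complete first week and 5.7% of the following 35 days (11.4% on a 24-hour reading). That follows from the documents alone.

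How much consumption is lost depends on the assumed taper. It is small at a 2-day half-life (91% of use recorded) and large at 10 days (44%). The understated percentage reduction also assumes an effect that begins at day 3; with a constant proportional effect from day 0, only the absolute saving is understated.

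This should be fixed before data collection, because the gap cannot be filled afterwards. It does not undermine VAS, the week-one opioid total or the comparisons on individual days.

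**What to change.** **Preferred.** At POD 14, 21, 28 and 42, keep the 12-hour question for the per-day comparison and state that window in both the protocol and the SAP. Add one item asking how many tablets have been taken since the last report, with the date of that report displayed. Define cumulative morphine equivalents as the sum of contiguous reports over POD 0-42: the 12-hour reports to POD 7 plus the four since-last-report counts, which cover 7 + 7 + 7 + 14 = 35 days. Leave the late 12-hour values out of this sum so that nothing is counted twice.

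**If the prompt is not changed.** Limit the cumulative total to POD 0-7, analyse the POD 14-42 values as 12-hour snapshots, and make no claim about total six-week consumption.

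**Cost.** One extra text item at four existing contacts and one SAP definition. Recall over 7 to 14 days is less exact than over 12 hours, so the total would mix two levels of precision. A check against remaining tablets is optional; it would need dispensed and refill quantities, which the documents do not describe collecting. The fallback needs no new data.
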